11.2 Sample Size Considerations

The primary outcome will be the surface-level primary molar caries increment ($d_{2-3mfs}/DMFS$) at two years post baseline, but the incremental dental caries at one year will also be compared between the two interventions. Based on the caries levels reported by [name] et al. (2010) and Chi et al. (2016) a conservative estimate for the coefficient of variation ($100 \times \text{standard deviation}/\text{mean}$) is 75%. Using a two-sided 0.025 significance level to control the type I error for testing at 1 and 2

years post baseline, 120 participants per intervention are required to demonstrate a 30% or greater reduction in caries in the test group as compared to the NaF varnish group with 90% power (van Belle and Martin, 1993; Champley, 2015). A 30% reduction by PVP-I + F⁻ versus NaF varnish alone was reported by Milgrom et al (2011) for any new caries (%), and a greater reduction would be expected in the amount of new caries in a high-risk caries population. To accommodate for attrition (up to 15%), although it is expected to be very low in the study population, a total of 280 participants will be enrolled.

11.3 Statistical Analysis Plan

11.3.1 Primary Statistical Analysis.

The primary analysis will be conducted in accordance with the intention-to-treat principle, and multiple imputation procedures will be used to account for missing caries information (Schafer, 1997). For the primary outcome, incremental dental caries based on d₂₋₃mfs/DMFS, the unit of analysis will be the child and the mean dental caries increment will be compared between the two interventions separately at 1 and 2 years post baseline using a two-sample t test assuming unequal variances. This approach assumes the distribution of dental caries increment is approximately symmetrical, which is often true in high-risk caries populations. In this case, non-symmetry, log-linear regression using robust standard errors, which can accommodate count outcomes with skewed distribution, will be used to compare the caries rates between the two interventions (Hardin & Hilbe, 2003). Covariate-adjusted linear (or log-linear) regression models using robust standard errors will be used to compare dental caries increment, adjusting for baseline dental caries, stratification variables (education center and school), gender and age of the participant (Hardin and Hilbe, 2003). Analyses will be performed using R (The R Foundation for Statistical Computing, 2016; Version 3.3.0) and SAS (SAS Institute, Cary, NC, Version 9.4).

11.3.2 Analysis of Safety Data.

Adverse events (AEs) will be tabulated by treatment group, severity, and perceived relationship to investigational product. For each AE, treatment group comparisons regarding the occurrence of at least one event will be made using Fisher's exact tests. The comparisons will be repeated excluding all mild symptoms. Similar analyses will be performed after grouping AEs by body system using standard Medical Dictionary for Regulatory Activities (MedDRA) coding. Individual AEs will be listed, with particular attention paid to serious AEs.

11.3.3 Participant Disposition.

The frequency and reasons for withdrawal will be summarized by treatment group, as will the number of missed visits and missed treatment applications (compliance).

12. Source Documents and Access to Source Data/Documents

The site will maintain appropriate medical and research records for this trial, in compliance with ICH E6, Section 4.9 and regulatory and institutional requirements for the protection of confidentiality of subjects.

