5.6 Treatment Assignment Procedures

5.6.1 Subject Identification Numbers

Participants will be randomly assigned to one of the two interventions with a 1:1 allocation as per a computer-generated randomization schedule with stratification on school and with randomly permuted blocks of sizes 2 and 4. Stratification and blocking will ensure the two interventions are equally balanced within school and randomly permuted blocks sizes will ensure concealment. The study biostatistician will create the randomization lists using the “sample” function of the R statistical software (Version 3.3.0; The R Foundation for Statistical Computing, 2016).

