8.1 Primary and Secondary Outcome Variables

Primary Outcome Variable

The primary outcome will be the surface-level primary molar caries increment ($d_{2-3}mfs/DMFS$) at two years post baseline, but the incremental dental caries at one year will also be compared between the two interventions. Only the statistician and sponsor will know of the one-year finding.

Secondary Outcome Variable:

Child response on the depicted Facial Image Scale (Buchanan & Niven, 2002) to the treatment will be recorded immediately after the initial treatment visit and after the fourth treatment visit.

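### Section 11.3.1 leaves the covariate-adjusted analysis of the primary outcome without a status; naming the already planned adjusted linear model as the single primary analysis would settle this and probably narrow the interval

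*Combined protocol and SAP*

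**What the plan says.** Section 11.3.1, headed as the primary statistical analysis, gives three approaches to one outcome.

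1. The mean increment is to be "compared between the two interventions separately at 1 and 2 years post baseline using a two-sample t test assuming unequal variances".
2. The t test is said to rest on approximate symmetry. Otherwise the plan switches to a model of caries rates: "In this case, non-symmetry, log-linear regression using robust standard errors, which can accommodate count outcomes with skewed distribution, will be used". It gives no criterion for non-symmetry and no date for the decision.
3. "Covariate-adjusted linear (or log-linear) regression models using robust standard errors will be used to compare dental caries increment". The covariates listed are caries at baseline, the strata (center and school), sex and age. These models are not called primary, secondary, supportive or sensitivity.

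No section names the effect measure to be reported. Section 11.2 states its target as a "30% or greater reduction in caries in the test group as compared to the NaF varnish group" and concludes that "a total of 280 participants will be enrolled"; section 5.1 allows up to 600. Randomisation is "with stratification on school and with randomly permuted blocks of sizes 2 and 4" (section 5.6.1). A baseline dental examination is scheduled (7.1), and age and sex are recorded at recruitment (7). On the one-year comparison, section 8.1 says: "Only the statistician and sponsor will know of the one-year finding". Section 14.4, however, keeps the sponsor blinded to treatment assignments until the whole study has ended.

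**The concern.** Two things are at stake.

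The first is precision. The apparent headline test ignores the randomisation stratum and baseline caries, although both will be in the database and a model using them is already planned. If baseline caries predicts the increment, the unadjusted interval is wider than it needs to be.

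The second is labelling. The adjusted and unadjusted models will give two p-values and two intervals for the same outcome, possibly on two scales, and no sentence says which one the trial is judged by. If that is settled after the one-year comparison, it may be settled by someone who has seen comparative data.

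**Working it through.** **Inputs from the documents.** Coefficient of variation 75%, 30% reduction, two-sided 0.025, 90% power, 120 per arm, 280 enrolled, attrition up to 15% (11.2); up to 600 enrolled (5.1); 1:1 allocation stratified by school in blocks of 2 and 4 (5.6.1); nine centers (5.5).

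**Assumptions.** The documents give no correlation between baseline caries and the increment. I take the share of variance explained by baseline (R²) as 0, 6.5 and 16%. The simulations also assume lognormal-Poisson counts, a control mean of 8, a school intraclass correlation of 0.05, no effect of age or sex, and no sibling correlation.

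**Step 1: reproduce the plan's figure.** Scale the control mean to 1 (SD 0.75), so the test mean is 0.70 (SD 0.525).

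n = (2.2414 + 1.2816)² × (0.75² + 0.525²) / 0.30² = 12.411 × 0.838125 / 0.09 = 115.6, so 116 per arm.

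The Welch test with the noncentral t needs 117 (power 90.0%). At 120 per arm power is 90.8%. The stated 120 therefore matches an unadjusted comparison of means.

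**Step 2: power with adjustment, closed form.** Multiply the variance by (1 − R²). After 15% loss, 280 becomes 238 (119 per arm) and 600 becomes 510 (255 per arm).

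| R² | 119 per arm | 120 per arm | 255 per arm |
|---|---|---|---|
| 0 (unadjusted) | 90.5% | 90.8% | 99.85% |
| 6.5% | 92.4% | 92.6% | 99.92% |
| 16% | 94.9% | 95.1% | 99.97% |

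The standard error shrinks by √(1 − R²): 0.967 at 6.5% and 0.917 at 16%.

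**Step 3: simulation at 238 analysed** (at least 6,000 replicates per setting under the alternative and 10,000 under the null).

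| R² | t test power | Adjusted, HC1 | Adjusted, HC3 | SE ratio to t test, HC1 | SE ratio to t test, HC3 |
|---|---|---|---|---|---|
| 0 | 91.0% | 91.1% | 89.9% | 0.99 | 1.02 |
| 6.5% | 90.4% | 92.6% | 91.7% | 0.96 | 0.99 |
| 16% | 91.1% | 95.7% | 95.0% | 0.90-0.91 | 0.93-0.94 |

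A second simulation at 238 gave HC1 standard-error ratios of about 0.99 / 0.97 / 0.91 and power gains of about nil / 1 / 4 points. Type I error of the adjusted linear model was 2.3-2.4% with HC1 and 1.9-2.1% with HC3.

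**Step 4: with multiple imputation** (280 randomised, 15% missing completely at random, 20 imputations from an assumed normal model, HC3). Power, t test versus adjusted: 88.3 v 88.4, 89.1 v 89.9 and 89.5 v 94.2%. The gains are 0.1, 0.9 and about 4.8 points, with a simulation standard error of about 0.7 on each power. The imputation model is my assumption, so these levels say nothing about whether the trial is underpowered.

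**Step 5: what if the smaller p-value were reported?** If the two test statistics are bivariate normal with correlation √(1 − R²), the chance under the null that either passes 0.025 is 3.2% at R² 6.5% and 3.5% at 16%. Simulation at 238 gave 2.5 / 3.0 / 3.2%; with imputation, 2.3 / 2.3 / 2.8%. A separate simulation at 120 per arm, with baseline as the only covariate, gave 3.1% at a correlation of 0.24 and 3.8-3.9% at 0.47 and 0.63, which are stronger than assumed above.

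**Step 6: the scale.** The unadjusted log-linear model tests the same equality of means. Its type I error was 2.4-2.6%, and it agreed with the t test in over 99% of simulated trials. The covariate-adjusted log-linear model is more delicate: at 238 with nine schools, an uncorrected sandwich variance gave up to about 3.4-3.5% against 2.5%, and a degrees-of-freedom correction brought this to 2.5-2.8%.

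**The case against.** The strongest reply is that the hierarchy can be read from the text. The t test is named first for the primary outcome, the log-linear model is its conditional fallback, and the adjusted models come last. The sample size matches the unadjusted test. That stands: the t test is the apparent primary analysis, and what is missing is the label.

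The benefit is also conditional. With R² of 0 and HC3 the adjusted model loses about 1 point of power and its interval is about 2% wider. With imputation, two of the three gains cannot be told from zero. If 600 enrol, power exceeds 99.8% either way. All of this stands and limits the claim to a likely, modest gain.

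Three stronger readings do not hold. A reader might infer that the smaller p-value will be chosen; no section says so, and under the assumed R² range the cost would be about 2-3.5% against 2.5%. A reader might infer that the symmetry switch inflates the error rate; for the unadjusted models it does not, and it only leaves the reported scale open. A reader might take it as settled that the sponsor will hold the one-year result when the choice is made; sections 8.1 and 14.4 conflict on this.

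**Conclusion.** The point holds as an improvement in efficiency and labelling. Nothing here shows that the trial is underpowered or the t test wrong: the plan's 120 per arm reproduces, and the test meets its stated power.

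With 238 analysed and HC1, making the adjusted linear model primary changes power by about nil / 1-2 / 4-5 points and narrows the interval by about 1 / 4 / 9% at R² of 0 / 6.5 / 16%. These sizes rest on the assumed R² and count distribution. The recommendation is worth adopting because the expected gain is positive unless baseline caries is close to uninformative, the possible loss is about 1 point, and it settles in advance which result counts. Confidence is medium because the documents do not show how prognostic baseline caries is. Siblings may enrol, but clustering by family was not evaluated here and is a separate point.

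**What to change.** In section 11.3.1:

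- Name one primary analysis at 24 months: the planned linear regression adjusted for baseline caries (on the same index as the outcome), school, age and gender. State a robust variance with a degrees-of-freedom correction, such as HC1 or HC3.
- Name the adjusted mean difference, with its confidence interval, as the effect measure. Remove the symmetry judgement as a route to a different primary scale.
- Fix all of this before the one-year comparison is run, and use the same model at one year.
- Label the unadjusted t test and the log-linear rate ratio as sensitivity analyses. The rate ratio speaks to the percentage reduction targeted in 11.2; its robust variance also needs a small-sample correction.

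Separately, reconcile sections 8.1 and 14.4 on whether the sponsor sees the one-year result.

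The cost is analysis-plan wording and a decision on the variance form. The sample size does not change and no new data are needed: school is the randomisation stratum, and baseline caries, age and sex are already collected.

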4.2 Rationale for Dosage

The treatment group will be exposed at baseline and once every three to four months after baseline for a maximum period of 24 months. The control group will be exposed to the control varnish in the same manner. The decision for dosing every three to four months with the test varnish was based on earlier work (Berkowitz, Koo et al. 2009) and the AAPD Standard of Care for children at high risk for dental caries.

5. Study Enrollment and Withdrawal

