7.3 Visits 2-8

- The visit will be at the Center
- The examiner will conduct the dental and oral examination at visits 4 and 8.
- A study assistant will retrieve the drug assignment and will apply the assigned agent
- The assistant will review and record concomitant medications
- The assistant will review and record adverse events

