7.4 Follow-Up Contacts

The subject's teacher will be contacted 48 hours following treatment. If the child is not attending or the teacher knows of a problem, the parent will be contacted to determine if there is a reportable AE. The medical monitor will assign causality. No treatments will be done on Fridays to avoid having to make home visits in order to obtain the basic AE information on the weekend.

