9.3 Adverse Events

An adverse event (AE) is any untoward medical occurrence associated with the use of a drug in humans, whether or not considered drug related. An AE can therefore be any unfavorable and unintended sign, symptom, or disease temporally associated with any use of a drug, whether or not related to the drug. An adverse event can arise from any use of the drug (e.g., off-label use, use in combination with another drug) and from any route of administration, formulation, or dose. This excludes minor fluctuations in signs or symptoms of the disease under study, but includes significant worsening of the disease. It also includes any apparently unrelated illness and any accident that occurs during participation in the study.

Some examples of adverse events are:

- Development of an illness during the study.
- Development of symptoms which may or may not be related to the use of a concomitant medication or investigational product.

All adverse events, whether observed by the Principal Investigator, elicited from or volunteered by the subject, subject's teacher or parent/guardian, should be recorded on the Adverse Event Log. This reporting will include a brief description of the event, the date of onset, the date of resolution, the duration and type of event, the severity, contributing factors, and any action taken with respect to the investigational product.

AEs occurring after informed consent is obtained but prior to randomization will be recorded as medical history, unless possibly related to a study procedure, in which case they will be recorded as adverse events in the case report form. New adverse events will be captured and reported on the AE log until 30 days following the last treatment or premature withdrawal, whichever comes first.

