9.6 Reporting Procedures

9.6.1 Reportable Events

The following incidents will be considered reportable events and will be reported to the Principal Investigator within 24 hours of the site's awareness of the event.

- Serious Adverse Event
- Emergency Treatment Disclosure
- Post-Treatment Adverse Events*, including
 - Nausea
 - Not eating
 - Vomiting
 - Difficulty swallowing or breathing
 - Swelling around the lips or skin on the face
 - Itchiness around the lips or skin of the face
 - Hives or rash

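### The planned adverse-event tests in 11.3.2 use no onset window and do not pool the listed post-treatment reactions, so they have little power for reactions that resemble ordinary childhood illness; one added comparison is a cheap improvement

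*Combined protocol and SAP*

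**What the plan says.** The safety analysis is in section 11.3.2: "For each AE, treatment group comparisons regarding the occurrence of at least one event will be made using Fisher's exact tests". The comparisons are repeated without mild symptoms and again after grouping by MedDRA body system. Events are tabulated by severity and perceived relationship, and individual events are listed. No time window is stated.

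The definition of an adverse event in 9.3 is broad: "It also includes any apparently unrelated illness and any accident that occurs during participation in the study". Collection is continuous: "New adverse events will be captured and reported on the AE log until 30 days following the last treatment", or until premature withdrawal if that is earlier. Section 4.2 has treatment given "once every three to four months after baseline for a maximum period of 24 months".

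The protocol already holds the elements of a more focused comparison. Section 7.4 says "The subject's teacher will be contacted 48 hours following treatment". Section 9.6.1 has a list headed "Post-Treatment Adverse Events*, including", which covers nausea, not eating, vomiting, difficulty swallowing or breathing, swelling, itchiness, and hives or rash. Section 9.3 records the onset date of each event, and 6.3 logs each application. Section 8.3 says that perceived relationship will be compared between the groups, but 11.3.2 names no method for this.

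**The concern.** Documenting the safety of the test varnish is a secondary objective (3.1). A reaction to a topical varnish would be expected soon after application. The planned tests ask only whether a child ever had a given event in about two years. Vomiting, poor appetite or rash from ordinary illness then adds events equally to both arms and can hide a modest excess from the varnish. Grouping by body system raises the background further. Testing term by term can also split one reaction across several small comparisons. The repeat without mild events does not help: 9.6.4 defines mild as no limitation of usual activities, which would take in many brief local reactions. At stake is a conclusion of no safety difference that the data already being collected might contradict.

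**Working it through.** **Plan's own figures.** The plan gives no power figure for safety. Its only sample-size calculation (11.2) is for caries: coefficient of variation 75% in each arm, 30% reduction, two-sided 0.025, 90% power. A noncentral t calculation gives 117 per arm against the stated 120, and 240/0.85 = 283 against the stated 280. This does not bear on the safety tests.

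**Inputs from the documents.** The total is up to 600 (5.1) or 280 (11.2), so 300 or 140 per arm. Less 15% attrition, that is 300 × 0.85 = 255 or 140 × 0.85 = 119. There are eight applications: the first treatment visit (7.2) and visits 2 to 8, where "A study assistant will retrieve the drug assignment and will apply the assigned agent" (7.3). Eight 48-hour windows make 16 of about 730 days, or 2.2%.

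**Assumptions, since the documents give none.** A proportion B of children has the event over the whole period for other reasons, spread evenly over time. An extra 4% of test-arm children react within 48 hours of an application, and all of this excess falls in the one endpoint tested. The test is two-sided Fisher at 0.05.

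**Formulas.** Whole period: control B, test 1 − (1 − B)(1 − 0.04). Window: control w = 1 − (1 − B)^(16/730), test 1 − (1 − w)(1 − 0.04). Power is exact, by enumerating both binomial distributions.

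**Results, 255 per arm:**

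| B | Whole period, control / test | 48-hour windows, control / test | Power, whole period | Power, windows |
|---|---|---|---|---|
| 0 | 0 / 4.0% | 0 / 4.0% | 94% | 94% |
| 1% | 1.0% / 5.0% | 0.02% / 4.0% | 70% | 94% |
| 5% | 5.0% / 8.8% | 0.11% / 4.1% | 34% | 91% |
| 10% | 10.0% / 13.6% | 0.23% / 4.2% | 20% | 88% |
| 20% | 20.0% / 23.2% | 0.49% / 4.5% | 12% | 81% |
| 40% | 40.0% / 42.4% | 1.1% / 5.1% | 7% | 68% |

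**119 per arm.** Windowed power runs from 34% at B = 0 to 26% at B = 40%. Whole-period power is 10%, 7% and 5% at B = 10%, 20% and 40%.

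**Splitting across terms, zero background, 255 per arm.** With no control events, five test events give p of about 2 × 0.5^5 = 0.06 and six give about 2 × 0.5^6 = 0.03, so six are needed. One composite expects 0.04 × 255 = 10.2 events and has 94% power. Split equally over two terms, power is 40% per term. Over three terms, at 10.2/3 = 3.4 expected events each, it is 13% per term.

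**If recorded background clusters after applications.** Suppose half of it falls in the windows, so w = 1 − (1 − B)^0.5. At B = 10% the arms are 5.1% and 8.9%, and power is 20% whole-period against 33% windowed. At B = 20% it is 12% against 19%.

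**Second set of assumptions, without attrition.** Take a 5% excess and 0.2 background episodes per child-year, so that 1 − exp(−0.4) = 33% of control children have an event in two years. At 300 per arm, power is 12% over the whole period, 93% in 48-hour windows and 70% in 7-day windows. At 140 per arm it is 7% against 53% for 48 hours.

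**The case against.** A reader might infer that any real varnish reaction would be swamped by colds and accidents. The documents do not support that. The tests are run for each event, so an unrelated illness or accident cannot dilute the test for hives or lip swelling. Section 9.4 names rash and swelling at the site of application as risks, and where the background of such a term is near zero the planned test has the same power as the windowed one. For a rare reaction confined to one term, the planned test may even do better than a composite of all listed symptoms, because the composite carries more background. This objection stands and limits the point.

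A reader might also infer that the plan ignores timing and relationship altogether. It does not. Relationship is tabulated, 8.3 promises a comparison, and the causality categories in 9.6.3 rest partly on timing. What remains is that 11.3.2 specifies no group test on either.

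The even-spread assumption is favourable to the window. Events are recorded at contacts (9.2), and the scheduled contacts are the 48-hour teacher contact and the treatment visits. Recorded background may therefore cluster after applications, which shrinks the gain, as the 20% against 33% case shows. The table also compares one endpoint with and without the window; the plan itself runs no 24-month composite, so its rows should not be read as the power of such a test.

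At the smaller sample size the added comparison would usually miss a 4% excess too. Events are captured until withdrawal, so deducting 15% is somewhat pessimistic, but the second set of assumptions shows the same pattern without it. Finally, the asterisk in 9.6.1 points to a footnote that is absent from the text available here and may define a period after treatment; its absence cannot be held against the plan.

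**Conclusion.** The point holds as a cheap improvement, not as a flaw that invalidates the safety analysis. For reactions that overlap with common childhood illness, for body-system groups and for a reaction spread over several terms, the planned tests lose much of their power. At 255 per arm with a 4% excess, the fall is from about 91% to 34% at 5% background and from 88% to 20% at 10%. At zero background there is no loss; at 1% power falls from 94% to 70%. All of these figures rest on assumed rates, an assumed 0.05 level and, except where stated, an even spread of background events. The whole-period reading is itself an inference from the absent window and the collection rule, though a sound one. None of this shows that the whole-period tests should be demoted. They address the stated hypothesis of no difference in the frequency of adverse events (11.1), and they are where later effects would be seen.

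**What to change.** Keep the tests planned in 11.3.2 and add two items:

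1. One prespecified comparison of the proportion of children with at least one reaction listed in 9.6.1, of any severity, with onset within 48 hours of any application. Report the risk difference with a confidence interval. The 48 hours follow the protocol's own contact time in 7.4; if the 9.6.1 footnote defines another period, use that.
2. A group comparison of events judged related to the product, with its method stated, to give effect to 8.3.

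The total of 280 in 11.2 and up to 600 in 5.1 should also be reconciled, because safety power depends on it.

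The cost is SAP wording, one derived variable from onset and application dates already recorded, and one more windowed safety comparison to interpret alongside the others. Reactions that start after 48 hours would be seen only in the whole-period tables.

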5.5 Strategies for Recruitment and Retention

Children attending Early Childhood Education programs in Pohnpei State will be enrolled. In 2015 there were 9 centers enrolling 597 children. Maximum enrollment will be children. We expect to be able to enroll the entire sample from Nett, Kolonia, Saladak, Awak, ESDM, Pohnpei Catholic, UCCP, Calvary Christian and St. Paul centers but will recruit from other

centers as required. Based on our previous work in Micronesian schools in the US affiliated states we expect nearly every parent to consent and thus for us to enroll the entire sample within two months (Milgrom et al., 2009; [name] et al., 2010; Milgrom et al., 2011).

The parent (or legal guardian) of the potential subject will be approached by a study assistant who will confirm eligibility of the subject. The proposed study will be explained. Written informed consent will be obtained. Up to 600 families will be enrolled.

The Micronesian islands are quite isolated and children do not change schools or move from the islands readily. We will regularly provide healthy snacks at the centers and hold end of year study parties for parents and children at the centers to reduce dropouts. Families whose children complete the first treatment visit will receive a \$35 gift card as an incentive. Families whose children complete a year in the study will receive another \$35 gift card; families whose children complete two years in the study will receive a third \$35 gift card. In addition, the children will receive a study backpack including a set of school supplies. To be more inclusive, all children in the programs will receive a free study t-shirt, irrespective of whether they are enrolled in the study. The incentive levels were determined based on advice from Department of Health. We have conducted two prospective cohort studies with a similar population in the islands. The one-year attrition rate was 1/172 (less than 1%) in one study and no child was lost to follow-up in the other study ([name] & Milgrom, 2010; Milgrom, [name] & Mancl, 2011).

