9.2 Methods and Timing for Assessing, Recording, and Analyzing Safety Parameters

Adverse events will be recorded at each contact with the teacher or parent.

Adverse events will be reviewed on a monthly basis by the Medical Monitor ([name]); serious adverse events and other protocol-specified reportable events will be assessed in real time by the Principal Investigator ([name]) and Site Director ([name]).

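### Adverse events are compared by pooled Fisher's exact tests although children are randomised within school; a test stratified by school would cost nothing and could be modestly more sensitive for common events

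*Combined protocol and SAP*

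**What the plan says.** Section 11.3.2 tabulates adverse events by arm, severity and perceived relationship. For each event, "treatment group comparisons regarding the occurrence of at least one event will be made using" Fisher's exact tests. The tests are repeated without mild events and again by MedDRA body system. School is not mentioned.

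Section 5.6.1 describes 1:1 allocation "with stratification on school and with randomly permuted blocks of sizes 2 and 4". Section 5.5 indicates how many strata to expect: "In 2015 there were 9 centers enrolling 597 children", with further centers to be added if needed.

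Events reach the record by several routes:
- Section 7.4: "The subject's teacher will be contacted 48 hours following treatment". A parent is contacted if the child is absent or the teacher knows of a problem.
- Section 9.2: "Adverse events will be recorded at each contact with the teacher or parent".
- Section 7.3, for visits 2-8: "The assistant will review and record adverse events".
- Sections 9.3 and 9.5.2 add events observed by the investigator or reported by the child, and staff assessment of clinical features.

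In section 11.3.1, school enters only the covariate-adjusted caries models. The t test named first there also ignores it.

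**The concern.** Balancing the arms within school removes differences between schools from the comparison of arms. A single 2x2 table over all schools puts those differences back into the reference distribution. If schools differ in how often events are recorded, the test's true error rate falls below its nominal level and it loses power.

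Such differences are plausible. Teachers belong to schools, and at 48 hours the teacher is the first filter for acute reactions. The assistant's review at the next visit comes three to four months after the previous application, so it is not a full substitute.

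Adverse event occurrence is a named secondary outcome (section 3.2.2), and section 11.1 hypothesises no difference in its frequency. A non-significant result may therefore be read as support for that hypothesis, so avoidable insensitivity is undesirable here.

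**Working it through.** **1. The plan's own figures.** The plan gives no event rate, significance level, power or margin for safety, so there is no safety calculation to reproduce. Its one sample-size calculation (section 11.2: coefficient of variation 75%, 30% reduction, two-sided 0.025, 90% power) does reproduce. A two-sample t test with standard deviations 0.75 and 0.525 of the control mean needs 117 per arm, against the stated 120. Allowing for 15% attrition, 120/0.85 = 141.2, so 142 per arm or 284 in total, against the stated 280. Section 5.1 allows up to 600. Both totals are used below; the documents need to reconcile them.

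**2. Mechanism.** Let p_s be the event probability in school s and p its mean, with no arm effect and equal schools. The pooled test works with a variance proportional to p(1−p). Under allocation within school, the arm difference has a variance proportional to the mean of p_s(1−p_s), which equals p(1−p) − Var(p_s). The overstated share is Var(p_s)/[p(1−p)]. If the relative spread between schools is c, so that Var(p_s) = c²p², the share is c²·p/(1−p). The factor p/(1−p) is:
- 0.02/0.98 = 0.020 at 2%
- 0.05/0.95 = 0.053 at 5%
- 0.20/0.80 = 0.250 at 20%

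For the same relative spread, the share at 20% is about 12 times that at 2%. Any loss therefore falls mainly on common events.

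**3. Size under assumptions.** Assumed, not in the documents: 9 equal schools, odds ratio 2, two-sided 0.05, control-arm rate averaged over schools held at 5% or 20%, and normal variation of school log-odds with SD 0, 0.7 or 1.2. Comparing a school one SD above average with one SD below, SD 0.7 means a 4-fold difference in odds (e^1.4) and SD 1.2 an 11-fold difference (e^2.4). There were 4,000 trials per setting, so the standard error of one power is at most √(0.25/4000) = 0.8 points. Power in %, pooled Fisher → exact test stratified by school (gain in points):

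| Children | Control rate | SD 0 | SD 0.7 | SD 1.2 |
|---|---|---|---|---|
| 280 | 5% | 23.8 → 24.0 (+0.2) | 21.0 → 22.0 (+1.0) | 17.4 → 20.1 (+2.7) |
| 600 | 5% | 50.6 → 50.6 (0.0) | 46.5 → 47.9 (+1.4) | 40.8 → 44.5 (+3.7) |
| 280 | 20% | 67.5 → 67.4 (−0.1) | 60.2 → 63.0 (+2.8) | 49.2 → 57.2 (+8.0) |
| 600 | 20% | 95.4 → 95.4 (0.0) | 91.7 → 92.8 (+1.1) | 81.8 → 86.9 (+5.1) |

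Other runs put the SD 1.2 gains at about 3 points for 5% and 5 to 7 points for 20%, so the last digit should not be pressed. At control rates of 1 to 2% (3,000 trials), gains were 0 to 0.4 points for SD up to 0.7 and 0.3 to 1.2 points at SD 1.2.

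At 20% and SD 1.2, the true type I error of Fisher's test is 2.5% (280 children) or 2.4% (600), against 3.9% or 4.0% stratified.

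**4. Unequal schools.** A second set used nine schools of unequal size, with control risks 2/5/10/30% and odds ratios 4/2.5/2/1.8. At SD 1.0 the gains were 2.6/2.8/3.8/6.9 points with 140 per arm and 0.5/2.1/2.8/3.8 with 300 per arm. At SD 0.5 no gain exceeded 2.2. The largest, 12.2 points, needed 30% risk, 140 per arm and SD 1.5.

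**5. How much is due to school?** With 140 per arm, 2% risk, odds ratio 4 and SD 1.0, Fisher's power is 40.8%. Stratifying exactly gives 43.4% (+2.6). An unstratified mid-p test, which ignores school, gives 50.4% (+9.6). At 30% risk, odds ratio 1.8 and the same SD, the figures are 45.5%, 52.4% (+6.9) and 50.8% (+5.3). For uncommon events the discreteness of Fisher's test costs more than pooling does, and an exact stratified test keeps that discreteness.

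**The case against.** The pooled Fisher test is valid and simple, and it matches the unstratified t test in section 11.3.1. The conservatism depends on school variation that no section quantifies, and an 11-fold difference in odds is extreme. Teachers are not the only source: the assistant's review, parents, the investigator and staff assessment are common to all schools, and a child's absence triggers contact with the parent whatever the teacher knows. Most of the planned tests concern single, probably uncommon events, where stratifying gains almost nothing.

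All of this stands. It limits the size and priority of the point but does not remove it: the mechanism follows from the design, and the change costs no measurable power when schools are alike.

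A reader might infer that the pooled test is known to be too conservative, or that real harms would go unnoticed. The documents support neither. They give no recorded event rates by school. No safety decision is tied to a Fisher p-value either: section 9.2 provides monthly medical review, section 9.6.1 requires listed reactions to be reported within 24 hours, and section 11.3.2 lists events individually.

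**Conclusion.** The point holds as a modest, conditional one. The safety test does not follow the randomisation, and it is conservative if, and only if, recorded event rates differ by school. The gain from stratifying is about zero if schools are alike and 0 to 1 point for events near 2%. It is about 1 point (SD 0.7) to 3 or 4 points (SD 1.2) near 5%. Near 20% it is 1 to 3 points (SD 0.7) or 5 to 8 points (SD 1.2).

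These sizes rest on the assumed number of schools, odds ratio, significance level, event rates and school variation; none of them is a planned operating characteristic of the safety analysis. There is no inflation of false positives. The benefit lies mainly with any adverse event, common events and body-system groups.

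**What to change.** In section 11.3.2, replace the pooled Fisher tests with the exact conditional (Cochran-Mantel-Haenszel) test stratified by school as randomised. Apply it to each event, to the repeat without mild events and to the body-system groups. Report the common odds ratio with its exact confidence interval; at present the section names only a test. Define the stratum as the unit used to build the randomisation list, because section 11.3.1 refers to both education center and school.

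The cost is one or two sentences. School is already recorded, R is already named as analysis software, and error control remains exact. Schools with no events contribute nothing and cause no difficulty. The priority is optional. Keeping Fisher's test and adding the stratified analysis for any adverse event, common events and body-system groups would secure most of the benefit.
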